10.4.2.3. Treatment States for COPD exacerbation

| Treatment State | Definition |
|---|--|
| Pre-Treatment | Exacerbations Onset Date < Study Treatment Start Date |
| On-Treatment | Study Treatment Start Date ≤ Exacerbations Onset Date ≤ Study Treatment Stop +1 |
| Post-Treatment | Exacerbations Onset Date > Study Treatment Stop Date+1 |
| Time to first on-treatment exacerbation | = Exacerbation Onset Date of first on-treatment exacerbation - Treatment Start Date +1 Missing otherwise. |
| Duration (Days) | Exacerbation resolution date or date of death – Exacerbation Onset Date + 1 |

NOTES:

- If the study treatment stop date is missing then the exacerbation will be considered to be On-Treatment.
- If the exacerbation onset date is missing or partial then the exacerbation will be considered on-treatment unless there is evidence to the contrary (e.g. the month of the onset date is present and is less than the month of the first dose of study treatment).
- Exacerbations reported by subjects who did not receive treatment will be considered pre-treatment.

10.5. Appendix 5: Data Display Standards & Handling Conventions

10.5.1. Study Treatment & Sub-group Display Descriptors

| Treatment Group Descriptions | | | |
|------------------------------|---------------|-----------------------------|----------------------|
| RandAll NG | | Data Displays for Reporting | |
| Code | Description | Description | Order ^[1] |
| A | UMEC 62.5 mcg | UMEC 62.5 mcg | 2 |
| P | Placebo | Placebo | 1 |

NOTES:

1. Order represents treatments being presented in TFL, as appropriate.

10.5.2. Baseline Definition & Derivations

10.5.2.1. Baseline Definitions

For all endpoints (expect FEV1 and FVC) the baseline value will be the latest pre-dose assessment at schedule visit. Unless otherwise stated, the mean of replicate assessments at any given time point will be used as the value for that time point.

The baseline value for FEV1 and FVC is calculated from the values measured 30 min and 5 min pre-dose on Day 1. If the actual time of an assessment is after the time of dosing on Day 1, the value at that assessment will be set to missing prior to calculating baseline. If one of the values is missing then the baseline will be the single remaining value; otherwise the baseline will be the mean of the two values.

10.5.2.2. Derivations and Handling of Missing Baseline Data

| Definition | Reporting Details |
|------------------------------|---|
| Change from Baseline | = On-treatment Value – Baseline value |
| % Change from Baseline | = $100 \times [(On-treatment Value - Baseline value) / Baseline value]$ |
| Maximum Change from Baseline | = Calculate the change from baseline at each given timepoint and determine the maximum change |

NOTES :

- Unless otherwise specified, the baseline definitions specified in Section 10.5.2.1 Baseline Definitions will be used for derivations for endpoints / parameters and indicated on summaries and listings.
- If either the baseline or on-treatment value is missing then the change from baseline will be set to missing.
- The change from baseline will not be calculated for baseline records or records prior to baseline

10.5.3. Reporting Process & Standards

| Reporting Process | |
|---|---|
| Software | |
| 
 The currently supported versions of SAS software will be used. | |
| Reporting Area | |
| HARP Server | : uk1salx00175 |
| HARP Area | : \arenv\arprod\gsk573719\ac4117410\final |
| QC Spreadsheet | : arenv\arprod\gsk573719\ac4117410\final\qc |
| Analysis Datasets | |
| 
 Analysis datasets will be created according to Integrated Data Standards Library standards. | |
| Generation of RTF Files | |
| 
 RTF files will be generated. | |

| Reporting Standards | |
|---|--|
| General | |
| 
 The current GSK Integrated Data Standards Library (IDSL) will be applied for reporting, unless otherwise stated: 
 4.03 to 4.23: General Principles 5.01 to 5.08: Principles Related to Data Listings 6.01 to 6.11: Principles Related to Summary Tables 7.01 to 7.13: Principles Related to Graphics | |
| Formats | |
| 
 All data will be reported according to the randomized treatment the subject received unless otherwise stated. However, there may be additional adhoc displays for individual subjects using the actual treatment received. GSK IDSL Statistical Principles (5.03 & 6.06.3) for decimal places (DP's) will be adopted for reporting of data based on the raw data collected. Numeric data will be reported at the precision collected on the eCRF. The reported precision from non eCRF sources will follow the IDSL statistical principles but may be adjusted to a clinically interpretable number of DP's. | |
| Planned and Actual Time | |
| 
 Reporting for tables, figures and formal statistical analyses : 
 Planned time relative to dosing will be used in figures, summaries, statistical analyses and calculation of any derived parameters, unless otherwise stated. Reporting for Data Listings: 
 Planned and actual time relative to study drug dosing will be shown in listings (Refer to IDSL Statistical Principle 5.05.1). Unscheduled or unplanned readings will be presented within the subject's listings. | |
| Unscheduled Visits | |
| 
 Unscheduled visits will not be included in summary tables except as part of a 'worst case post-baseline' assessment. | |

| Reporting Standards | |
|---------------------------------------|--|
| | 
• Unscheduled visits will not be included in figures.• All unscheduled visits will be included in listings. |
| Descriptive Summary Statistics | |
| Continuous Data | Refer to IDSL Statistical Principle 6.06.1 |
| Categorical Data | N, n, frequency, % |
| Graphical Displays | |
| | 
• Refer to IDSL Statistical Principles 7.01 to 7.13. |

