- Perform liver event follow up assessments, and monitor the subject until liver chemistries resolve, stabilize, or return to baseline values as described below.
- Withdraw the subject from the **study** (unless further safety follow up is required) after completion of the liver chemistry monitoring as described below.
- Do not restart with investigational product.

In addition, for criterion 1:

- Make every reasonable attempt to have subjects return to clinic **within 24 hours** for repeat liver chemistries, liver event follow up assessments (see below), and close monitoring
- A specialist or hepatology consultation is recommended
- Monitor subjects twice weekly until liver chemistries (ALT, Aspartate Aminotransferase (AST), alkaline phosphatase, bilirubin) resolve, stabilize or return to within baseline values

For criteria 2, 3, 4 and 5:

- Make every reasonable attempt to have subjects return to clinic **within 24 to 72 hrs** for repeat liver chemistries and liver event follow up assessments (see below)
- Monitor subjects weekly until liver chemistries (ALT, AST, alkaline phosphatase, bilirubin) resolve, stabilize or return to within baseline values; criterion 5 subjects should be monitored as frequently as possible.

Subjects with ALT ≥ 5 xULN and < 8 xULN which exhibit a decrease to ALT ≥ 3 xULN, but < 5 xULN and bilirubin < 2 xULN without hepatitis symptoms or rash, and who can be monitored weekly for 4 weeks:

- Notify the GSK medical monitor within 24 hours of learning of the abnormality to discuss subject safety
- Can continue investigational product
- Must return weekly for repeat liver chemistries (ALT, AST, alkaline phosphatase, bilirubin) until they resolve, stabilize or return to within baseline
- If at any time these subjects meet the liver chemistry stopping criteria, proceed as described above
- If, after 4 weeks of monitoring, ALT < 3 xULN and bilirubin < 2 xULN, monitor subjects twice monthly until liver chemistries normalize or return to within baseline values.

For criteria 1 to 5, make every attempt to carry out the **liver event follow up assessments** described below:

- Viral hepatitis serology including:
 - Hepatitis A Immunoglobulin M (IgM) antibody;
 - Hepatitis B surface antigen and Hepatitis B Core Antibody (IgM);
 - Hepatitis C RNA;
 - Cytomegalovirus IgM antibody;
 - Epstein-Barr viral capsid antigen IgM antibody (or if unavailable, obtain heterophile antibody or monospot testing);
 - Hepatitis E IgM antibody

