8.2. Clinical Laboratory Analyses

8.2.1. Overview of Planned Clinical Laboratory Analyses

The safety analyses will be based on the Modified Intent-To-Treat population, for the analysis on all countries overall and on China Modified Intent-To-Treat population for the analysis on China subgroup alone, unless otherwise specified.

Table 8 provides an overview of the planned analyses, with further details of data displays being presented in [Appendix 14: List of Data Displays](#). All the planned study population analyses will be done on all countries overall, and China subgroup alone (with the exception of those displays specified by country).

Table 8 Overview of Planned Clinical Laboratory Analyses

| Endpoint | Absolute | | | | Change from Baseline | | | |
|--|----------|---|------------|---|----------------------|---|------------|---|
| | Summary | | Individual | | Summary | | Individual | |
| | T | F | F | L | T | F | F | L |
| Chemistry | | | | | | | | |
| Laboratory Values | | | | | | | | |
| Clinical Chemistry | Y | | | | Y | | | |
| Clinical Chemistry values outside the normal range | Y | | | Y | | | | |
| Clinical Chemistry change from baseline value relative to the normal range | Y | | | | | | | |
| Clinical Chemistry maximum post-baseline value | | Y | | | | Y | | |
| Clinical Chemistry minimum post-baseline value | | Y | | | | Y | | |
| Hematology | | | | | | | | |
| Hematology | Y | | | | Y | | | |
| Hematology values outside the normal range | Y | | | Y | | | | |

| Endpoint | Absolute | | | | Change from Baseline | | | |
|--|----------|---|------------|---|----------------------|---|------------|---|
| | Summary | | Individual | | Summary | | Individual | |
| | T | F | F | L | T | F | F | L |
| Hematology change from baseline value relative to the normal range | Y | | | | | | | |
| Hematology maximum post-baseline value | | Y | | | | Y | | |
| Hematology minimum post-baseline value | | Y | | | | | Y | |
| Urinalysis | | | | | | | | |
| Urinalysis data | | Y | | | Y | | | |
| Hepatobiliary (Liver) | | | | | | | | |
| Liver Event | | | | | Y | | | |

NOTES:

- T = Table, F = Figures, L = Listings, Y = Yes display generated, PCI = Potential Clinical Importance
- Summary = Represents TFL related to any summaries (i.e. descriptive statistics) of the observed raw data.
- Individual = Represents FL related to any displays of individual subject observed raw data.

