- If a laboratory value which is expected to have a numeric value for summary purposes, has a non-detectable level reported in the database, where the numeric value is missing, but typically a character value starting with '<x' or '>x' (or indicated as less than x or greater than x in the comment field) is present, the number of significant digits in the observed values will be used to determine how much to add or subtract in order to impute the corresponding numeric value.
 - Example 1: 2 Significant Digits = '< x' becomes x – 0.01
 - Example 2: 1 Significant Digit = '> x' becomes x + 0.1
 - Example 3: 0 Significant Digits = '< x' becomes x – 1

Vital Signs

- The baseline value for a vital sign endpoint will be the most recent recorded value for that endpoint before dosing on Day 1 at schedule visit.
- The 'maximum/minimum post-baseline' value will be the maximum value for pulse rate and systolic blood pressure, or the minimum value for diastolic blood pressure, recorded at any scheduled, unscheduled or EW visit made after the start of study treatment.

12-Lead ECG

- The baseline value for an ECG endpoint will be the most recent recorded value for that endpoint before dosing on Day 1 at schedule visit.
- A 'maximum post-baseline' QTc(F), QTc(B), PR interval and heart rate value will be derived as the maximum value recorded at any scheduled, unscheduled or EW visit made after the start of study treatment.
- QTc(F) values (including 'maximum post-baseline') will be categorised as follows:
 - ≤ 450 msec
 - > 450 to ≤ 480 msec
 - > 480 to ≤ 500 msec

12-Lead ECG

> 500 msec.

- Change from baseline QTc(F) values (including change to 'maximum post baseline') will be categorised as follows:
 - < -60 msec
 - ≥ -60 to < -30 msec
 - ≥ -30 to < 0 msec
 - ≥ 0 to < 30 msec
 - ≥ 30 to < 60 msec
 - ≥ 60 msec.
- An 'any time post-baseline' ECG interpretation will be derived as the worst interpretation recorded at a scheduled, unscheduled or EW visit made after the start of study treatment. The order of severity from worst to best for ECG interpretation is: abnormal: clinically significant, abnormal: not clinically significant, normal, unable to interpret.
- Any ECG abnormality recorded by a subject with an ECG interpretation of 'abnormal: clinically significant' after the start of study treatment will be included in an 'any-time post-baseline' record of ECG abnormalities.

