10.8. Appendix 8: Values of Potential Clinical Importance**10.8.1. Laboratory Values**

Threshold values for liver function test results, which are considered values of potential clinical importance, are:

- 3 times the upper limit of normal (ULN) for Alanine Aminotransferase (ALT)
- 2 times the ULN for Total Bilirubin (BILT).

Graphical displays of liver function test results will be produced as described in Section 8.2 (Clinical Laboratory Analyses) to identify any results above the thresholds.

Laboratory values will be flagged relative to the normal range. Clinical concern ranges will not be used.

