10.14.9. Safety Figures

| Safety : Figures | | | | | | |
|------------------|--------------------|--------------|-------------------------------|---|-------------------|------------------------|
| IMCT No. | China Subgroup No. | Population | IDSL / TST ID / Example Shell | Title | Programming Notes | Deliverable [Priority] |
| 3.1. | 3.1 | Modified ITT | DB2114634 7.01 | Scatter Plots of Maximum Post Baseline versus Baseline for Chemistry Parameters with an Upper Limit of Normal Range | | SAC |
| 3.2. | 3.2 | Modified ITT | DB2114634 7.02 | Box Plots of Change from Baseline to Maximum Post-baseline for Chemistry Parameters with an Upper Limit of Normal Range | | SAC |
| 3.3. | 3.3 | Modified ITT | DB2114634 7.03 | Scatter Plots of Minimum Post Baseline versus Baseline for Chemistry Parameters with a Lower Limit of Normal Range | | SAC |
| 3.4. | 3.4 | Modified ITT | DB2114634 7.04 | Box Plots of Change from Baseline to Minimum Post-baseline for Chemistry Parameters with a Lower Limit of Normal Range | | SAC |
| 3.5. | 3.5 | Modified ITT | DB2114634 7.05 | Scatter Plots of Maximum Post Baseline versus Baseline for Haematology Parameters with an Upper Limit of Normal Range | | SAC |
| 3.6. | 3.6 | Modified ITT | DB2114634 7.06 | Box Plots of Change from Baseline to Maximum Post-baseline for Haematology Parameters with an Upper Limit of Normal Range | | SAC |
| 3.7. | 3.7 | Modified ITT | DB2114634 7.07 | Scatter Plots of Minimum Post Baseline versus Baseline for Haematology Parameters with a Lower Limit of Normal Range | | SAC |
| 3.8. | 3.8 | Modified ITT | DB2114634 7.08 | Box Plots of Change from Baseline to Minimum Post-baseline for Haematology Parameters with A Lower Limit of Normal Range | | SAC |
| 3.9. | 3.9 | Modified ITT | DB2114634 7.09 | Trellis Display of Maximum Post-baseline versus Baseline for Liver Function Test Parameters | | SAC |
| 3.10. | 3.10 | Modified ITT | DB2114634 7.10 | Least Squares Means Change from Baseline (95% CI) in Pre-dose Pulse Rate (bpm) | | SAC |

| Safety : Figures | | | | | | |
|------------------|--------------------|--------------|-------------------------------|---|-------------------|------------------------|
| IMCT No. | China Subgroup No. | Population | IDSL / TST ID / Example Shell | Title | Programming Notes | Deliverable [Priority] |
| 3.11. | 3.11 | Modified ITT | DB2114634 7.11 | Least Squares Means Change from Baseline (95% CI) in Pre-dose Systolic Blood Pressure (mmHg) | | SAC |

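### SAP 10.5.3 keeps unscheduled visits out of every figure, but maximum and minimum post-baseline laboratory values are planned only as figures, so those plots can understate peaks and the QTc(F) plots can disagree with their tables

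*SAP*

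**What the plan says.** SAP 10.5.3 sets two rules for unscheduled visits side by side. For tables: "Unscheduled visits will not be included in summary tables except as part of a 'worst case post-baseline' assessment". For figures: "Unscheduled visits will not be included in figures". The second carries no exception. Listings take all unscheduled visits.

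In SAP 8.2.1, Table 8, the row "Clinical Chemistry maximum post-baseline value" and the matching rows for chemistry minima and for haematology are marked for figures, with no table or listing. Appendix 14 agrees. Figures 3.1 to 3.8 plot the maxima and minima, and Figure 3.9 is the "Trellis Display of Maximum Post-baseline versus Baseline for Liver Function Test Parameters". Tables 3.26 to 3.33 contain no maximum or minimum.

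SAP 10.8.1 sets 3xULN for ALT and 2xULN for total bilirubin, gives graphical displays the task "to identify any results above the thresholds", and rules out clinical concern ranges.

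For ECG, SAP 10.6.3 says that the maximum post-baseline QTc(F) "will be derived as the maximum value recorded at any scheduled, unscheduled or EW visit made after the start of study treatment". Figures 3.13 and 3.14 plot that variable and its change from baseline; Tables 3.42 and 3.43 categorise them.

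Protocol Table 5 schedules post-baseline chemistry at Visit 6 (Day 84), Visit 8 (Day 168) and Early Withdrawal (EW). Protocol 6.3.4 adds repeat liver tests outside that schedule. For stopping criterion 1 the instruction begins "Monitor subjects twice weekly until liver chemistries", with weekly draws for the other criteria and for subjects who stay on treatment under monitoring.

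**The concern.** A maximum post-baseline plot exists to show the worst value each subject reached. With two planned draws in 24 weeks, the values taken because something looked wrong are mostly unscheduled, and the figure rule removes exactly those. If the programmer follows the text, the liver plots can show a subject lower than he or she actually was, or below a threshold that was crossed, in the display the SAP names for finding such crossings. For QTc(F), a figure and a table of the same variable could be built from different data with nothing in the SAP to explain the difference.

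**Working it through.** The plan states no number on this point, so the check sets the provisions against each other.

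| Item | Are unscheduled values allowed? | Source |
|---|---|---|
| Worst-case values in summary tables | Yes, by express exception | SAP 10.5.3 |
| Any figure | No, no exception | SAP 10.5.3 |
| Low/normal/high class at any post-baseline visit | Yes, with EW, up to two weeks after last dose | SAP 10.6.3, laboratory |
| Maximum or minimum laboratory value | Not defined | SAP 10.6.3 is silent |
| Maximum QTc(F) | Yes, with EW | SAP 10.6.3, ECG |
| Listings | Yes | SAP 10.5.3 |

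**Laboratory figures.** SAP 10.6.3 gives no definition of the laboratory maximum or minimum, so nothing specific displaces the general figure rule. The derivation it does give for any post-baseline visit is a class against the normal range, which cannot show 3xULN or 2xULN. No table by multiple of ULN is listed. The planned summary display of these thresholds is therefore graphical and, read literally, uses scheduled values only.

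**Count of draws.** Scheduled post-baseline chemistry for a completer: Day 84 + Day 168 = 2 values. A subject monitored weekly for 4 weeks on continued treatment under protocol 6.3.4 adds 4 unscheduled values. Of 2 + 4 = 6 values, 2 can reach the figure.

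**What can be missed.** The repeat draws in protocol 6.3.4 start from ALT of at least 3xULN.

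- If a scheduled draw triggers them, that draw is already at or above the ALT threshold and is plotted there. Missing are any later rise and any later bilirubin value. Illustration with assumed values: ALT 3xULN and normal bilirubin on Day 84, then ALT 6xULN and bilirubin 2.3xULN at an unscheduled repeat. From these two draws the plots keep 3xULN and normal bilirubin.
- If the elevation is first seen at an unscheduled draw, such as the additional safety samples allowed by protocol 6.3.3, and has settled by the next scheduled draw, the crossing is absent altogether.

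**QTc(F).** SAP 10.6.3 puts unscheduled and EW readings into the maximum. Tables 3.42 and 3.43 may use them under the table exception. Figures 3.13 and 3.14 may not use the unscheduled ones under the figure rule. Both instructions cannot be followed for those two figures.

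**EW.** SAP 10.6.3 names EW separately from unscheduled visits, so the figure rule does not itself exclude EW values. SAP 10.7.1 confines stand-alone EW data to worst-case use in tables and does not mention figures. Their place in these plots is unsettled.

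**The case against.** The best reply is that a derived maximum is not a visit, and that a specific derivation normally governs over a general display standard. For QTc(F) that is a fair way to resolve the conflict, so a mismatch between figures and tables is possible rather than certain. For laboratory maxima there is no specific derivation to invoke. The table rule also counts against it: the authors thought worst-case values needed an express exception there and wrote none for figures. The display shells and the sponsor's graphics standards are not in the documents, so actual programming practice cannot be checked.

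The second reply is that little is lost, and much of this stands. A reader might infer more than the documents support:

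- *That unscheduled elevations drop out of the comparison by arm.* They do not. The any-visit rows described in SAP 10.6.1 and 10.6.3 count unscheduled highs in the normal-range summaries. ALT of at least 3xULN with bilirubin of at least 2xULN is an SAE when more than 35% is direct or fractionation is unavailable (protocol 6.3.5.2), and so enters the SAE tables. The gap is in multiples of ULN.
- *That Figure 3.9 is the plan's combined ALT and bilirubin display.* Its title says maximum against baseline. Nothing shows that it crosses the two analytes.
- *That the loss can be sized by how often a transient elevation would span Day 84 or Day 168.* That describes the visit schedule. An elevation with no draw is absent whatever the figure rule says. The relevant quantity is how often an unscheduled value exceeds all scheduled ones, and the documents give nothing from which to estimate it.
- *That a mildly raised scheduled ALT leads to protocol repeats.* A value such as 2.6xULN triggers none under 6.3.4; a further sample would be discretionary.

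**Conclusion.** The point holds as a drafting fault with a limited safety-reporting consequence. Taken literally, SAP 10.5.3 leaves unscheduled values off Figures 3.1 to 3.9, which can understate peaks or miss a threshold crossing first seen at an unscheduled draw. It also contradicts the QTc(F) definition behind Figures 3.13 and 3.14. The size cannot be put as a rate; it depends on how many subjects have an unscheduled value more extreme than their scheduled ones. Individual values stay in the listings, including Listing 24 for out-of-range chemistry and Listing 51 for liver events. Efficacy inference is not affected. The conclusion assumes that the figure rule is applied as written and that no unseen shell overrides it. It deserves correction before unblinding because a stated rule produces a poorer safety display than the SAP itself intends.

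**What to change.** 1. In SAP 10.5.3, replace the figure bullet with: *Unscheduled visits will not be included in figures except figures of maximum or minimum (worst case) post-baseline values (Figures 3.1-3.9, 3.13, 3.14).*
2. State that EW values are also included in these figures, and align SAP 10.7.1 with that.
3. In the laboratory part of SAP 10.6.3, define maximum and minimum post-baseline as taken over any scheduled, unscheduled or EW value after the start of study treatment, up to two weeks after the last dose. The end limit matters: it is the one already used for the any-visit laboratory classes. Carrying over the ECG wording, which has no such limit, would put laboratory figures and tables on different windows. Later follow-up draws stay in the listings.

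The cost is a few SAP sentences. No new data are needed, and the ECG worst-case derivation is already specified. A table of ALT and bilirubin by multiple of ULN and arm would be a useful optional addition.
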